7.1 Therapeutic Parameters (for both arms of the study)

1. Prestudy scans and x-rays used to assess all measurable or non-measurable sites of disease must be done within **4 weeks** (28 days) prior to randomization/registration.
2. Prestudy CBC (with differential and platelet count) should be done **4 weeks** (28 days) before randomization/registration.
3. All required prestudy chemistries, as outlined in Section 3, should be done **4 weeks** (28 days) before randomization/registration unless specifically required on Day 1 as per protocol.

Rev. 8/11

Procedure	Prior to registration (≤ 28 days) ¹	10-14 days prior to starting Treatment or Observation	< 24 hours prior to starting Treatment or Observation	Induction- At the end of each Treatment or Observation cycle	Day 1 of each cycle	Studies needed to confirm sCR or CR	Periodically during Treatment or Observation	At study discontinuation or progression (whichever comes first)	28 Days after discontinuation of treatment	Post treatment to 10 years from study entry ¹¹
History and exam ⁶	X			X				X		X
Bone Marrow Aspirate and Biopsy ⁹	X					X				
ECOG Performance Status	X			X				X		X
NYHA Classification	X									
Chemistry labs ³	X			X				X		X
CBC with differential ⁴	X			X				X		X
Serum light chain assay	X			X		X		X		X
Serum immunoglobulin G, A, M	X			X				X		X
QOL ⁷	X			X				X		X

	SPEP	X			X				X		X
	Serum M-protein immunofixation	X					X				
	24 hr UPEP	X			X ^{2,10}				X ^{2,10}		X ^{2,10}
	Urine M-protein immunofixation	X					X				
	Metastatic bone survey	X						X ¹²	X		X ¹²
	ECG (12-lead)	X									
	Serum Pregnancy test for FCBP ⁵	X	X ⁵	X ⁵	X ⁵				X ⁵	X ⁵	
Rev. 8/11	Patient Education and Counseling ¹⁴	X		X	X	X			X	X	
	Serum Beta-2 microglobulin	X							X		
	C-reactive protein	X									
	LDH	X									
Rev. 8/11	Dispense lenalidomide ¹⁵			X		X					
Rev. 7/14	TSH (ARM A ONLY) ¹⁶	X									X ¹³
	Ultrasound ⁸				X						
	Documentation of oral drug				X						
	MRI (spine and pelvis)	X									
Rev. 12/13	Biological Sample Submissions	See Section 7.2									

1. Registration test results can be used for cycle 1 if less than 7 days before starting cycle 1.

-
2. If serum and urine M-components are measurable, both must be followed in order to evaluate response. Measurable levels of monoclonal protein (M-protein) are defined as ≥ 1.0 g/dL on serum protein electrophoresis or ≥ 200 mg 24hr of monoclonal light chain on a 24-hour urine protein electrophoresis; results must be obtained with 4 weeks prior to randomization.
- Rev. 8/11 3. Chemistry includes sodium, potassium, calcium, magnesium, phosphorus, blood urea nitrogen (BUN), creatinine, creatinine clearance, glucose, alkaline phosphatase, total bilirubin, aspartate aminotransferase (AST), and alanine aminotransferase (ALT). Magnesium and phosphorus is not required but should be tested as clinically indicated.
4. Hematology (CBC with differential) includes WBC, ANC, Platelets, Hgb, and Hct required for protocol therapy must be done < 24 hours prior to the treatment cycle.
- Rev. 8/11 5. Pregnancy tests for females of childbearing potential for patients on Arm A only. A female of childbearing potential (FCBP) is a sexually mature female, regardless of sexual orientation or whether they have undergone tubal ligation, who: 1) has not undergone a hysterectomy or bilateral oophorectomy; or 2) has not been naturally postmenopausal for at least 24 consecutive months (i.e., has had menses at any time in the preceding 24 consecutive months). Pregnancy tests (sensitivity of 25 mIU/mL) must occur within 10 – 14 days and again within 24 hours prior to initiation of lenalidomide. FCBP with regular or no menstruation must have a pregnancy test weekly for the first 28 days and then every 28 days while on therapy (including breaks in therapy); at discontinuation of lenalidomide and at Day 28 post the last dose of lenalidomide. Females with irregular menstruation must have a pregnancy test weekly for the first 28 days and then every 14 days while on therapy (including breaks in therapy), at discontinuation of lenalidomide and at Day 14 and Day 28 post the last dose of lenalidomide (see [Appendix VI](#)).
6. Clinical exam should look for plasmacytoma.
7. QOL timepoints: At registration (+ 7 days) prior to initiation of treatment or observation; the last day (+ 7) of cycles 6, 12, 18, 24, 30, 36, 42, and 48; and at the end of treatment or observation (+14 days). For patients that discontinue protocol therapy or go off observation early not due to disease progression, QOL will also be assessed at the next quarterly Long Term follow-up visit (+ 14 days). After this, patients will not be followed further for QOL.
8. If leg swelling or pain is present in legs, an ultrasound of the legs will be done for deep vein thrombosis.
9. Bone marrow biopsy or aspirate performed to evaluate plasma cells %, presence of sheets of plasma cells and presence of plasma cell clonality. Absence of plasma cell clonality required for sCR.
10. Needed if urine M-spike at study entry was ≥ 200 mg/24 hr or if VGPR needs to be documented.
11. Patients will be followed for progression every 3 months if patient is < 2 years from study entry, every 6 months if patient is 2-5 years from study entry, every 12 months if patient is 6-10 years from study entry. No specific requirements if patient is more than 10 years from study entry. Patients will be followed for survival only once progression occurs and study treatment ends.
12. To be repeated every year or if clinically indicated for progression or symptoms.
13. To be assessed every 4 months.
14. All patients must be counseled about pregnancy precautions, risks of fetal exposure and other risks. The counseling must be done on Day 1 of each cycle (or at a minimum of every 28 days) and at drug discontinuation. The Lenalidomide Education and Counseling Guidance Document ([Appendix VII](#)) must be completed and signed by a trained counselor at the participating site prior to each dispensing of lenalidomide treatment. A copy of this document must be maintained in the patient records. A Lenalidomide Information Sheet ([Appendix VIII](#)) will be supplied to each patient receiving lenalidomide treatment. The patient must read this document prior to starting lenalidomide study treatment and each time they receive new supply of study drug.
- Rev. 8/11 15. Only enough lenalidomide for 28 days or one cycle of study treatment may be provided to the patient each cycle.
- Rev. 8/11 16. TSH should be tested for Arm A ONLY and then only when clinically indicated by the Principal Investigator.
-

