6.3.2 Timing of QOL Assessments

The QOL assessment utilizing the FACT PWB+FWB and the MMS instruments will first be administered at registration (+ 7days) prior to initiation of treatment or observation. During the treatment or observation period, QOL will be measured every 6 cycles (day end + 7 days) up to cycle 48 and at the end of treatment (+ 14 days). For patients who discontinue protocol therapy or go off observation early not due to disease progression, QOL will also be assessed at the next quarterly Long Term follow-up visit (+ 14 days). After this, these patients will not be followed further for QOL.

7. Study Parameters for Arm A and Arm B

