9.7 Quality of Life

9.7.1 Primary QOL Endpoints

Quality of life assessment is performed in an identical fashion in both arms A and B and will be administered to both arms on the same schedule and frequency. The QOL assessment utilizing the FACT-

FWB+PWB and MMS instruments will first be administered at registration (+ 7 days) prior to initiation of treatment or observation. During the treatment or observation period, QOL will be measured every 6 cycles (day end + 7 days) and at the end of treatment or observation (+ 14 days). For patients that discontinue protocol therapy or go off observation early not due to disease progression, QOL will also be assessed at the next quarterly Long Term follow-up visit (+ 14 days). After this, these patients will not be followed further for QOL. Patients will be asked to complete the QOL questionnaire just prior to meeting with health care providers at scheduled visits. This should reduce the impact of health care related information upon perceived QOL.

The FACT-FWB+PWB PRO instrument has 14 items and the score ranges from 0-56. The primary endpoint for the QOL study will be defined as the mean change of the FACT-FWB+PWB score from registration (prior to randomization) to cycle 24. The null hypothesis is that the FACT-FWB+PWB mean change score between the two groups is the same over this time period. Based on the length of this PRO instrument, a minimal absolute difference in means change scores of the two arms of 4-6 is considered clinically significant between two groups.(70) Nevertheless, for this analysis the difference in drug-related QOL must be much greater to overcome a significant PFS benefit. The FACT- FWB+PWB domains are reported to have a standard deviation (SD) of 11. (Personal Correspondence with [name] dtd 12.26.08)

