Differences in FACT-FWB+PWB mean change scores between the treatment arms from time of registration to cycle 24 that can be detected with 80% power are presented in following table. The expected hazard rates on each arm served to establish patients alive without PD at the end of the interval. Sensitivity for the % of patients alive without PD (n=55 patients given expected hazard rates) assumed to complete the questionnaire at the end of cycle 24 (compliance rates of 55%, 70%, 85%), allowing for slightly more variability in the instrument (11.0, 12.0) and assuming different correlation (0.4, 0.6, 0.8) between repeated measures was performed. For example, assuming a SD of 11.0 for the FACT-FWB+PWB, a correlation between repeated measures of 0.6 and using a two-sided t-test with a 0.05 significance level, there is sufficient power to detect a true difference in the FACT-FWB+PWB mean change score between the two arms of 7.3-9.2. Given our chosen interval for the primary endpoint and the reduced sample size with the redesign, we will only be able to detect large differences in mean change score between arms at expected compliance rate (70%).

Differences detected with 80% power between Treatment Arms in Mean Change Score from Registration to end of Cycle 24: FACT-FWB+PWB					
standard deviation (SD)	correlation	SD of change	55% compliance n=30	70% compliance n=38	85% compliance n=56
11.0	0.4	12.05	11.2	9.9	9.0
	0.6	9.84	9.2	8.1	7.3
	0.8	6.96	6.5	5.7	5.2
12.0	0.4	13.15	12.2	10.8	9.8
	0.6	10.73	10.0	8.8	8.0
	0.8	7.59	7.1	6.2	5.7

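### QOL forms stop one quarterly visit after a non-progression exit, and 9.7.1 does not fix an adjusted, all-forms analysis for the cycle-24 comparison of lenalidomide with observation

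*Combined protocol and SAP*

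**What the plan says.** **Collection.** Under 6.3.2, 7.1 footnote 7 and 9.7.1, QOL is taken at registration, every 6 cycles to cycle 48, and at the end of treatment or observation. After an exit not due to progression there is one further form at the next quarterly visit. Then 6.3.2 says "After this, these patients will not be followed further for QOL", and footnote 7 says "After this, patients will not be followed further for QOL".

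**Visits.** Non-progressed patients are still seen after exit. Footnote 11 of 7.1 sets progression visits 3-monthly to year 2, then "every 6 months if patient is 2-5 years from study entry". After progression, "Patients will be followed for survival only once progression occurs and study treatment ends".

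**Primary QOL endpoint.** Section 9.7.1 defines it as the "mean change of the FACT-FWB+PWB score from registration (prior to randomization) to cycle 24", compared between arms. Its power example rests on patients free of progression: "The expected hazard rates on each arm served to establish patients alive without PD at the end of the interval". The only test named is in that example, "using a two-sided t-test with a 0.05 significance level", with one compliance rate for both arms. On clinical relevance, "a minimal absolute difference in means change scores of the two arms of 4-6 is considered clinically significant".

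**Missing data.** Section 9.7.2 names a method that models scores and time to dropout jointly, because much QOL data is expected to be missing. The wording is general. It stands under the secondary endpoints, after a mixed model comparing progressed with non-progressed patients, and 9.7.1 does not refer to it.

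**The concern.** Section 1.6.2 chose cycle 24 because patients would by then have met both acute and chronic toxicity. Yet the collection rule removes the cycle-24 score of R patients whom toxicity has taken off drug. These patients still attend visits, so the schedule causes the loss, not loss of contact. Obs patients may also leave early, but not for drug toxicity.

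Section 9.7.1 does not say how such patients, or those who progress or die, enter the comparison under objective 2.3.1. Two analysts could follow the text and report different primary QOL results: a t-test on completers, or a joint model using every form. The example also takes raw change from baseline, which is less precise than adjusting for the baseline score.

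**Working it through.** **1. The plan's own figures.**
- SD of change at SD 11 and correlation 0.6: 11 × √(2 × (1 − 0.6)) = 9.84, as tabled.
- Progression-free at 24 months, 90 per arm, hazards from 9.4: Obs 90 × exp(−0.0279 × 24) = 46; R 90 × exp(−0.011 × 24) = 69. Their harmonic mean is 55, which matches the n = 55 in 9.7.1 as a per-arm figure.
- The detectable differences do not reproduce. With 38 per arm, SD 9.84, 80% power and two-sided 0.05, I get 6.4, not 8.1. That is a separate matter and nothing below depends on it.

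**2. Who has no cycle-24 score.** Three months is 3 × 30.44 / 28 = 3.26 cycles, and 24 − 3.26 = 20.7. A patient who exits before about cycle 21 has the last form before cycle 24 ends.

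**3. Bias of a completer comparison if the target is progression-free patients** (the population 9.7.1 uses for sizing). Let q be the share of progression-free patients without a score after exit, and d their score deficit relative to stayers (positive = worse).

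Bias (R − Obs, positive favours R) = qR × dR − qO × dO

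The documents give none of these inputs. Under assumed values:
- qR 0.30, dR 8, qO 0.10, dO 0: 2.4 − 0 = +2.4.
- qR 0.30, dR −4 (better off drug), qO 0.10, dO 4: −1.2 − 0.4 = −1.6.
- Rate pairs (qR, qO) of (0.20, 0.05), (0.30, 0.10), (0.40, 0.10) and (0.30, 0.30), with dR from −4 to 8 and dO from 0 to 8: −3.6 to +3.2.
- No difference between exits and stayers: 0.

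**4. The same if the target is all randomised patients.** 24 cycles = 672 days = 22.08 months. From the medians in 9.4, S(Obs) = exp(−(ln 2 / 24.8) × 22.08) = 0.540 and S(R) = exp(−(ln 2 / 62) × 22.08) = 0.781. So 46.0% and 21.9% have had a PFS event. Taking non-progression exits on R only, with deficits dT (off drug) and dP (progressed):

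Bias = 0.781 × q × dT − 0.242 × dP

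- q 0 to 50%, both deficits 0 to 6: from −0.242 × 6 = −1.45 to 0.781 × 0.5 × 6 = +2.34.
- q 50%, dT −6, dP 6: −2.34 − 1.45 = −3.8.
- With equal deficits the sign changes at q = 0.242 / 0.781 = 31%.

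This formula treats every PFS event as a living patient with a missing score. At the 3-year survival assumed in 9.5 (79% and 91%), deaths by 22.08 months would be 1 − 0.79^(22.08/36) = 13.5% on Obs and 1 − 0.91^(22.08/36) = 5.6% on R. It is a rough guide only.

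**5. Does using all forms help?** I simulated SD 11, correlation 0.6, 6-point deficits, planned PFS hazards, toxicity exits uniform before cycle 21, and each visit regressed on earlier scores within arm. The 9.7.2 joint model was not simulated.

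| Scenario | Completers | All forms |
|---|---|---|
| Progression deficit only | −1.45 | about −0.5 |
| Lasting off-drug deficit, q 20% | +0.95 | about +0.3 |
| Lasting off-drug deficit, q 50% | +2.37 | about +0.4 |
| Recovery after the last form, q 20% | 0 | −0.6 |
| Recovery after the last form, q 50% | 0 | −1.9 |

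**6. Baseline adjustment.** Residual variance (1 − ρ²) against 2(1 − ρ) for change gives a ratio of (1 + ρ)/2: 0.80 at ρ = 0.6, and 0.70 to 0.90 over the plan's range of 0.4 to 0.8.

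**7. Timing of extra forms.** Cycles 24, 30, 36, 42 and 48 end at 22.1, 27.6, 33.1, 38.6 and 44.2 months. The nearest visits are at 21, 30, 36, 36 and 42 months, so the gaps are 1.1, 2.4, 2.9, 2.6 and 2.2 months. Accrual began in February 2013 (9.1). If it ended after 45 months (9.4, November 2016), the last cycle-24 and cycle-48 dates are about September 2018 and July 2020. If it ended 24 months after June 2015 (9.2), they are about May 2019 and March 2021. The adverse event list in 5.3 is dated June 2019.

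**The case against.** **The plan never commits to a completer test.** This stands. The t-test appears only in a power illustration, and the 9.7.2 wording could cover all QOL data. A reader might infer that 9.7.1 specifies a completer analysis. It does not; the text leaves the method open.

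**The direction is not known.** This also stands. A reader might infer that losing patients with toxicity flatters R. That needs them to score worse than stayers at cycle 24, whereas they may recover off drug. Losing more Obs progressors pushes the other way, but only if the target is all randomised patients, and 9.7.1 sizes on those free of progression. The 5% and 10% crossover figures in 9.4 are not toxicity-stop rates and cannot settle it.

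**The effect is small for this endpoint.** Largely right. The illustrative biases are below the 4-6 point threshold, 9.7.1 concedes that only large differences are detectable, and it requires more than the threshold to offset a PFS benefit.

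**The remedy is not shown to be better in every case.** True. All-forms analysis is worse if scores recover after the last form, and the joint model was not tested. That is why the completer result belongs alongside.

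**Extra collection comes late.** Probably so for cycle 24.

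What survives is that the collection rule creates an avoidable, arm-specific loss at the primary timepoint, and that baseline adjustment is a gain in precision at no data cost.

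**Conclusion.** The point holds as a minor one. The stop rule is clear in three places and removes the cycle-24 score of R patients who stop for toxicity before about cycle 21, although they are still being seen. Section 9.7.1 does not say whether the joint model governs the comparison between arms.

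A completer comparison, if used, would be biased to the extent that exits differ from stayers. Under assumed rates and deficits this runs to a few points either way (−3.6 to +3.2 for progression-free patients), and it is zero if they do not differ. The documents supply no exit rate by arm and no score difference, so neither sign nor size can be claimed. The firm number is the variance ratio of 0.80 from baseline adjustment, which rests on the plan's correlation of 0.6. The PFS analysis is not touched.

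**What to change.** **(a) Section 9.7.1, before QOL data are analysed.**
- Analyse the R versus Obs difference at cycle 24 in a longitudinal model with baseline FACT-FWB+PWB as a covariate, using every collected form, including end-of-treatment and quarterly forms.
- State the target population and how stopping therapy, progression and death are handled.
- State whether the 9.7.2 joint model applies.
- Report alongside it the completer change-score comparison and an analysis that shifts missing scores over a stated range including zero.

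**(b) Sections 6.3.2, 7.1 and 9.7.1.** For any patient whose assessment times have not passed, continue QOL after a non-progression exit at the follow-up visits already scheduled, analysed at actual time. By the plan's accrual dates this is probably too late for cycle 24 and would serve only later timepoints, under objective 2.3.2.

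**Cost.** Part (a) is text and analysis of forms already collected. Part (b) needs an amendment and a few extra 28-item questionnaires, and only later enrollees would contribute. The joint model rests on dropout assumptions that the data cannot test. Baseline adjustment improves precision but does not cure dropout.

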5.1 Administration Schedule

5.1.1 Arm A Lenalidomide*

Lenalidomide 25 mg by mouth days 1-21 every 4 weeks (28 days).

Aspirin (or alternative prophylaxis) days 1-28 for each treatment cycle. Suggested dose is 325 mg/day, however the dose is at the discretion of the treating physician. Alternative dosing of 75mg/day or higher is acceptable provided the patient is at low risk of thrombosis.

All patients on Arm A are required to receive prophylaxis against thrombosis. For patients in Arm A, physicians should consider prophylaxis with aspirin alone as studies with single agent lenalidomide in the setting of relapsed disease show a relatively low incidence of thrombosis (< 5%). See Section [5.5.2.1](#) for acceptable alternative prophylaxis.

Treatment continues until progression to symptomatic myeloma or discontinuation due to toxicity.

For patients with CrCl 30-60 mL per minute, lenalidomide dose is 10 mg per day for days 1-21 every 28 days. Creatinine clearance (CLcr) can either be measured CLcr or estimated by the Cockcroft-Gault method: $\{[140 - \text{age (yrs)}] \times [\text{lesser of IBW (kg) or actual weight (kg)}]\} / [72 \times \text{serum creatinine (mg/dL)}]$; multiply by another factor of 0.85 if female.

* **NOTE:** The first 44 patients to accrue will be placed on Arm A without randomization (Phase II).

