5.1.2 Arm B Observation

Observation continues until progression to symptomatic myeloma.

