Venous Thrombosis/embolism ≥ Grade 3	Hold (interrupt) dose and start anticoagulation; restart at investigator's discretion after adequate anticoagulation (maintain dose level).	Omit lenalidomide for remainder of cycle and start anticoagulation. Restart at investigator's discretion after adequate anticoagulation (maintain dose level).
Hepatic or other Non-hematologic toxicity Assessed as lenalidomide- Related ≥ Grade 3	Hold (interrupt) dose and follow. If the toxicity resolves to grade 1 prior to Day 21 restart at next lower dose level and continue the cycle until Day 21.	Omit lenalidomide for remainder of cycle.
Hyperthyroidism or Hypothyroidism	Omit lenalidomide for remainder of cycle, evaluate etiology, and initiate appropriate therapy. Restart lenalidomide next cycle (decrease dose by one dose level).	Omit lenalidomide for remainder of cycle, evaluate etiology, and initiate appropriate therapy. Restart lenalidomide next cycle (decrease dose by one dose level).

As noted in the table above, lenalidomide can be introduced after resolution of certain toxicities, midway through the cycle, provided the toxicity resolves prior to day 21. If drug needs to be held at the time of retreatment for adverse events, then the date of when treatment is resumed is considered day 1 of new treatment cycle. Patients requiring a treatment delay beyond 6 weeks will end protocol treatment.

If lenalidomide is held for an entire cycle and toxicity resolution does not occur within this time, lenalidomide dosing should be permanently stopped.

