5.7 Duration of Follow Up

For this protocol, all patients, including those who discontinue protocol therapy early, will be followed for response until progression and for survival for 10 years from the date of randomization. All patients must also be followed through completion of all protocol therapy, and until PD, even if they initiate non-protocol therapy.

6. Measurement of Effect

Definitions of Stringent Complete Response, Complete Response, Very Good Partial Response, Partial Response, and Stable Disease are based on International Uniform Response Criteria for Multiple Myeloma and the American Society of Hematology/Food and Drug Administration consensus panel recommendations for the assessment of disease progression.(64)

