6.2.6 Progression (PD)

The investigation that qualified as progression should be repeated and verified on a subsequent occasion only if treating physician deems it clinically necessary. Patients will be considered to have progression if both of the following criteria are met.(64)

1. Any one or more of the following:
 - Increase in serum M-protein to $\geq 25\%$ above the lowest response level, which must also be an absolute increase of at least $0.5\text{g}/\text{dl}$ to qualify as “progression.”
 - Increase in urine M-protein to $\geq 25\%$ above the lowest response level for 24-hour excretion, which also must be an absolute increase of at least $200\text{mg}/24$ hours of urine M-protein to qualify as “progression.”
 - Increase in bone marrow plasma cell percentage to $\geq 25\%$ from lowest response value (the absolute % increase must be $\geq 10\%$).

AND

2. Any one or more of the following felt related to the underlying clonal plasma cell proliferative disorder:
 - Hypercalcemia ($> 11 \text{ mg}/\text{dL}$)
 - Decrease in hemoglobin of $\geq 2 \text{ gms}/\text{dL}$

- Serum creatinine level \geq 2mg/dL
- Development of myeloma bone lesions or soft tissue plasmacytoma.

If subsequent verification is done, progression should be recorded as the date when the abnormality was first detected, not the date when it was confirmed.

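### Does the unstated PFS censoring date, with sparser progression checks once a patient is off protocol treatment, put the primary test at risk?

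*Combined protocol and SAP*

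**What the plan says.** The schedule table in Section 7.1 places the examination, chemistry, blood count and SPEP under a column headed "At the end of each Treatment or Observation cycle", for both arms. Footnote 11 governs the post-treatment column, where patients are "followed for progression every 3 months if patient is < 2 years from study entry, every 6 months if patient is 2-5 years", with longer gaps after that. The footnote names no arm.

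The routes off protocol differ. Section 5.1.1, on Arm A: "Treatment continues until progression to symptomatic myeloma or discontinuation due to toxicity". Section 5.4 adds: "Patients requiring a treatment delay beyond 6 weeks will end protocol treatment". Section 5.1.2, on Arm B: "Observation continues until progression to symptomatic myeloma". However, Sections 5.6.1 to 5.6.5 include withdrawal of consent and use of non-protocol therapy among the reasons to stop. Footnote 7 to the same table provides for patients who "discontinue protocol therapy or go off observation early not due to disease progression".

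Patients who stop stay in the primary analysis. Section 5.7: "All patients must also be followed through completion of all protocol therapy, and until PD, even if they initiate non-protocol therapy". On dating, where a progression is later verified, Section 6.2.6 says "progression should be recorded as the date when the abnormality was first detected".

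Section 9.4 defines PFS failure and specifies Kaplan-Meier curves, a stratified log-rank test, intention to treat and six looks ending at 76 events. It gives no censoring date for event-free patients and no analysis of assessment timing.

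**The concern.** A progression is recorded when someone looks for it. A patient seen every 28 days has an average lag of about half a cycle; a patient seen every six months may wait much longer. If more lenalidomide patients are on the sparse schedule, their progressions are dated later, and more of them are still unfound when the database is cut. If event-free patients are then counted as progression-free up to the cut, Arm A gains follow-up time in which no event could have been recorded. Both effects favour lenalidomide even if the drug does nothing. Section 11.1 says the trial will support a US marketing application, so an inflated type I error or a censoring rule chosen after seeing the data would matter.

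**Working it through.** **Inputs from Section 9.4.** 90 per arm, 45 months of accrual, 9 months of further follow-up, observation median 24.8 months (hazard 0.0279), target hazard ratio 2.5, 76 events, one-sided 0.025.

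**The plan's own figures reproduce.**
- Power in the Freedman form: √76 × (2.5 − 1)/(2.5 + 1) = 8.718 × 0.4286 = 3.74. Then 3.74 − 1.96 = 1.78, which gives 96.2% against the stated 96%.
- Expected events at month 54 under the alternative: 76.2 against 76.
- The six nominal levels together spend 0.0249.

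**Size of the lag.** Half of a 28-day cycle is 0.46 months, in line with the simulated mean lag of 0.45 months in Arm B with nobody leaving. In Arm A the mean lag of counted events is 0.64 to 0.79 months. The excess is 0.19 to 0.34 months, or 0.8% to 1.4% of a 24.8-month median. Progressions not yet found at the cut come on top of this.

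**Type I error, run 1** (20,000 null trials per scenario, standard error about 0.001; off-protocol visits on the footnote 11 calendar from study entry; unstratified log-rank). Stopping rates are assumptions.

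| Off protocol by month 24 (Arm A / Arm B) | Found at onset | Data-cut censoring |
|---|---|---|
| 0% / 0% | none | 0.025 |
| 30% / 0% | none | 0.031 |
| 50% / 0% | none | 0.036 |
| 30% / 10% | none | 0.030 |
| 50% / 10% | none | 0.033 |
| 50% / 10% | half | 0.028 |
| 50% / 50% | none | 0.025 |

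With last-assessment censoring the same run gives 0.026 to 0.029, and 0.023 when half of progressions are found through symptoms. On the six-look boundary with 50% of Arm A stopping, it is 0.035 (data cut) against 0.028 (last assessment), and 0.024 with no stopping.

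**Type I error, run 2** (30,000 null trials per scenario; off-protocol visits counted on from the stopping date). The last column analyses the same simulated patients as if every onset date were known exactly.

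| Arm A / Arm B off | Found at onset | Data cut | Last assessment | Exact onset |
|---|---|---|---|---|
| 30% / 0% | none | 0.033 | 0.028 | 0.028 |
| 50% / 0% | none | 0.034 | 0.025 | 0.024 |
| 70% / 0% | none | 0.040 | 0.026 | 0.026 |
| 50% / 10% | 20% | 0.031 | 0.025 | 0.024 |

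Within simulation error, last-assessment censoring performs as well as knowing every onset date. A null median of 40 months gives the same picture (data cut 0.030 to 0.041, last assessment 0.024 to 0.027).

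**A fuller detection model.** Footnote 12 sets the bone survey yearly, or when clinically indicated, both on and off treatment, and deaths have exact dates. Suppose 20% of events are dated at onset and 30% are found at an annual survey, with 10% of Arm B leaving (again assumptions; 12,000 trials, standard error about 0.0015). Data-cut error is then 0.029 or 0.032 with 30% or 50% of Arm A stopping. If 30% of Arm A and 20% of Arm B leave, with 20% of events dated at onset, it is 0.025.

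**Estimate when the true hazard ratio is 2.5.** The mean is 2.50 with no stopping, 2.54 to 2.60 with data-cut censoring (up 1.6% to 4%) and 2.51 to 2.54 with last-assessment censoring (up 0.4% to 1.6%).

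**The case for a change.** The best case for a change is that the censoring rule alone decides whether there is a bias, and the plan leaves it open in a trial meant for a marketing application. At the top of run 1 the inflation is 0.036 − 0.025 = 0.011, or 44% of the nominal level, and 70% stopping takes it to about 0.04. Section 5.7 does not help, because it tells sites how long to follow patients and does not tell the analyst where to censor. Sections 9.4 and 9.7.2 already provide for crossover and for informative dropout in quality of life, so one sentence on PFS would cost little.

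The omission stands, and so does the direction of the effect under data-cut censoring. The size does not carry the case. The top figures need data-cut censoring, stopping rates with no source in the documents, nobody leaving observation, and no event found between visits. The plan itself points away from the third condition: Section 5.6 and footnote 7 foresee early exits from either arm, and Section 9.4 considers 5% to 10% of each arm crossing over. Exits from both arms offset each other, fully so in the 50%/50% run.

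An interval-censored sensitivity model would add little. It gives 0.024 to 0.025 under the null, but it turns slightly conservative (0.020, null hazard ratio 0.99) when half of progressions are found through symptoms. It was also tried only as an exponential model on exponential data.

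**Conclusion.** This is missing detail that an analyst fills sensibly. A data-cut date is not a date on which anyone established that the patient was progression-free; the last disease assessment is. An analyst who censors there gets a type I error of about 0.023 to 0.029 across the scenarios in both runs, and a mean hazard ratio estimate within 2% of the truth.

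Even with the less suitable choice, 30% to 70% of Arm A stopping shifts the mean log-rank Z by 0.09 to 0.19 (run 2, nobody leaving Arm B). The Z expected at the design effect is about 3.7, so only a result very close to the boundary could be affected.

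The visit schedule applies the same rule to both arms, the stated power and event count reproduce, and no stated rule gives a wrong answer. Writing the censoring date down would be harmless, but it would only record the ordinary default and leave the primary test as it is.

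The conclusion rests on assumed stopping rates, exponential PFS, an unstratified test in the simulations, and the expectation that analysts censor at the last assessment.
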